With regard to study design, we will ensure the same treatment dose within and across treatment conditions (Pain Coping Skills Training vs Arthritis Education). We will monitor session attendance for coping skills training and arthritis education using a diary log with participant ID numbers and session dates to track percentage of attendance and to account for absenteeism and reasons for missed sessions. We will make every effort to deliver the full treatment, but we expect some variation in treatment delivery dose as well as treatment drop-out. Reasons for attrition will be assessed with an open-ended question for enrolled participants who withdraw. Drop-out reasons will be categorized and then judged by independent raters. Comparisons between the treatment conditions in drop-out rates will be made, and these rates will be included as covariates in the planned analyses if significant between-group differences emerge.

Loss to follow-up is always a threat in longitudinal studies. The following strategies will be employed to minimize loss to follow-up: (1) we will use up to 8 phone attempts to contact participants to schedule their post-treatment assessments; (2) we will obtain alternative phone contact information from each participant; (3) if we fail to contact a participant during follow-up phone contacts, despite multiple phone attempts, we will mail a reminder letter; (4) participants will receive up to \$150 remuneration for study participation and this remuneration will distributed throughout the study period to be commensurate with study demands; and (5) we inflated our sample size by 20% to account for possible attrition.

Additional retention strategies will be employed in the study to reduce loss to follow-up as much as possible. For example, study coordinators will personally meet each patient enrolled in the study to develop rapport with each patient. The study website developed by the data coordinating center will provide study coordinators at each site with red-flag notices when patients miss their scheduled appointment dates by more than 48 hours. Study coordinators will be required to contact patients with missing data within 24 hours of receiving a red-flag notice. The PI will receive weekly reports from the data coordinating center so that the study investigators can discuss recruitment and retention during bi-weekly conference calls.

Preliminary Studies

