Thus, the total required sample size is 321 (107 patients per arm) for the planned 3-arm trial. Based on our pilot study, we expect 5% attrition due to early drop-out resulting from cancelled surgery. Patients who undergo surgery and drop out due to lack of interest, unrelated medical illness or loss of follow-up also will be included in the intent to treat analysis. Our pilot study of 18 patients suggests this number will be on the order of 10%, although this estimate is likely to be low because the pilot study was only 2 months in duration. Our previous work with similar types of patients suggests that loss to follow-up will likely be closer to 20% one year following surgery.^{14,29} Therefore, 402 patients (134 patients per study arm) will need to be enrolled in the trial (321+64 due to loss of follow-up+17 due to cancelled surgery). A total of 2,100 patients will need to be screened because our pilot studies indicated that approximately 19% of the screened sample will actually participate (ie. they will meet all inclusion and exclusion criteria AND provide consent for the study). Stratification by surgeon and by site is expected to reduce outcome variability and thereby increase power.

Data Analysis

Intention to treat (ITT) will be the primary approach for all analyses and, depending on the pattern of missing data (missing at random, completely at random or not missing at random), multiple imputation using SAS StAT/MI methods will be used to impute values for those lost to follow-up.¹³³ In addition, we will compare the ITT analysis to the results for patients who actually undergo surgery to determine if undergoing surgery affects the findings. For the primary analysis, the effect of treatment will be assessed using linear mixed models with time as a repeated factor. The model will account for correlation over time within participants, correlations within clinics, surgeons, and baseline covariates. Surgical approach, complications, medication and physical therapy use will be assessed for potential effects.

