Estimates of the effect of pain coping skills training will be obtained by constructing linear contrasts to compare the mean change in outcome from baseline to each of the key time points (2 months, 6 months and 1 year) between the pain coping skills group and the two control groups, with adjustment for the other variables. Analyses of the secondary outcome variables will be conducted using a similar approach. For the analyses using dichotomous outcomes of $\geq 50\%$ improvement at 6 months and 12 months, generalized linear models with logistic regression will be used to compare the proportion of patients with $\geq 50\%$ improvement after adjustment for baseline data.

Our study is powered to detect clinically important differences in WOMAC Pain scores among treatment groups. As an additional secondary analysis, we also will examine the effects of potential moderators. Moderators are baseline characteristics that predict treatment effects.¹³⁴ Additional psychosocial issues may influence treatment effects in knee arthroplasty patients with high levels of pain catastrophizing. Potential

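### The rule adding drop-out rates as covariates when arms differ is wrong as written: nothing keeps it out of the primary 1-year pain contrast

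*Combined protocol and SAP*

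**What the plan says.** The rule is in Steps to Enhance Treatment Fidelity and Reduce Potential Biases. That paragraph aims for equal dose "across treatment conditions (Pain Coping Skills Training vs Arthritis Education"), and continues: "We will monitor session attendance for coping skills training and arthritis education using a diary log". It expects some treatment drop-out, records why enrolled participants withdraw, and compares drop-out between the conditions. It then commits that "these rates will be included as covariates in the planned analyses if significant between-group differences emerge". It does not say which test triggers the rule, at what level, whether a rate belongs to an arm or a patient, or whether drop-out means stopping sessions or leaving the study.

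Data Analysis says "Intention to treat (ITT) will be the primary approach for all analyses" and that, depending on the missing-data pattern, "multiple imputation using SAS StAT/MI methods will be used to impute values for those lost to follow-up". The primary analysis uses "linear mixed models with time as a repeated factor", with baseline covariates and clinic and surgeon correlation. The contrasts of mean change from baseline are "between the pain coping skills group and the two control groups, with adjustment for the other variables". Drop-out is not named as a covariate there, but the list is not closed and the earlier rule is not withdrawn. Sample Size Estimations adds that patients who have surgery and then "drop out due to lack of interest, unrelated medical illness or loss of follow-up also will be included in the intent to treat analysis".

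**The concern.** Randomisation protects comparisons that use only assignment and variables fixed before it. Drop-out is neither, and the trigger brings it into the model in exactly those trials where the arms differ on it. An analyst following the text would apply the rule to the primary contrast. At stake is Hypothesis 1a (training vs education): its estimate could become unobtainable, or could compare patients of like drop-out status instead of patients as randomised. Whether Hypothesis 1b (training vs usual care) is touched depends on a scope that the text leaves open.

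**Working it through.** **The plan's own figure.** Inputs from Sample Size Estimations: 107 per arm, difference 2.0, SD 4.34, two-sided 0.05. The ratio 2/(4.34 × √(2/107)) is 3.37, so power is Φ(3.37 − 1.96) = 92.1%, or 91.9% by the noncentral t. The plan states 91%, which reproduces. The covariate rule does not enter that calculation.

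**Reading 1: one rate per arm.** With three arms the fixed-effect columns are an intercept, two arm indicators and the rate. The rate is fixed once the arm is known, so the rank is 3 of 4 (2 of 3 with two arms). The arm effect cannot be separated from the rate.

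**Reading 2: session drop-out.** Usual care has no study sessions, so the covariate has no value there. In one three-arm model, Hypothesis 1b then has no defined adjustment. If the rule covers only the two session arms, 1a is affected and 1b is not.

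**Reading 3: a patient-level indicator.** Let d_T and d_C be the drop-out proportions and γ the fitted pain difference between drop-outs and others within arm. In a one-time-point least-squares fit, adjusted minus unadjusted pain difference = −γ(d_T − d_C). This is zero when the proportions are equal or γ is zero.

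Assume a latent drop-out propensity with the same distribution in both arms, correlation r with 1-year pain, and arm-specific cut-points. With φ the normal density at each cut-point:

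γ = r × 4.34 × (φ_T + φ_C) / [d_T(1 − d_T) + d_C(1 − d_C)].

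The rates below (training vs education) and r = 0.2 to 0.5 are assumptions. The documents give only about 20% loss to follow-up at 1 year, not split by arm.

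- 25% vs 12%: γ = r × 4.34 × (0.3178 + 0.2000)/(0.1875 + 0.1056) = 7.67r, or 1.53 to 3.83 points. The spurious benefit is 0.13γ = 0.20 to 0.50 points.
- 30% vs 10%: γ = r × 4.34 × (0.3477 + 0.1755)/(0.21 + 0.09) = 7.57r. The spurious benefit is 0.20γ = 0.30 to 0.76 points.
- 12% vs 25%: the sign reverses. A true 2.0 points is estimated at about 1.8 to 1.5.
- 20% vs 20%: zero.

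Simulating the two-step rule in this model (107 per arm, all 1-year scores observed, no true effect, drop-out test at p < 0.05) gives one-sided false benefit of about 4.5 to 11% at 25% vs 12%, against a nominal 2.5%. At 20% vs 20% it is 2.2 to 2.6%.

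**Trigger.** The plan names no test. With 27 of 134 (20%) lost in one arm, an uncorrected chi-square test reaches significance at 41 of 134 in the other (p = 0.049). Fisher's test needs 43 (p = 0.037).

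**The same indicator in repeated-measures models.** Assumptions: 134 per arm, between-visit correlation 0.5, loss after 6 months related to the 6-month score, no true effect, trials where the rule fired. Positive values favour training, which loses more patients.

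| Model | 25% vs 12%, r = 0.2 to 0.5 | 30% vs 10%, r = 0.5 |
|---|---|---|
| Post-baseline visits only, 1-year contrast | about 0.1 to 0.26 | about 0.38 |
| Baseline among the outcomes, change contrast, complete data | 0 | 0 |

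The zeros are algebraic. A time-constant indicator moves an arm's baseline and 1-year means by the same amount, −γ times the arm's drop-out proportion, so the change is untouched. With loss after 6 months the cancellation is no longer exact, and the change contrast shifts by about −0.05 to −0.12 points across these cases, against the arm that loses more. Simulation error is about 0.02 points.

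**The case against.** The strongest reply concerns the model. Data Analysis describes a repeated-measures analysis with contrasts of change from baseline. If baseline is one of the repeated outcomes, a main-effect indicator drops out with complete data, and with losses the small shift has the opposite sign to the single-time-point result. That stands, and it rules out any general statement about direction. The single-time-point figures also give every drop-out an observed 1-year score and apply drop-out within 107 per arm, the number left after allowing for loss. They therefore describe session drop-out with complete follow-up, not loss to follow-up. The larger imbalances are assumed.

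A second reply is that the clause sits in a fidelity section, near treatment drop-out in the two session arms, and that intention to treat is declared primary. The narrow scope is plausible, but training vs education is itself a primary hypothesis. The intention-to-treat statement settles who is analysed; it does not say that the covariate rule stops short of the primary model.

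A reader might infer that the rule removes patients from the intention-to-treat set, or that it always flatters the arm with more drop-out. Neither is supported: drop-outs after surgery are expressly kept in, and direction depends on the model. Nor do the documents show that the rule would fire.

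**Conclusion.** The concern holds as a fault in the written rule: a post-randomisation variable, undefined in unit, type, test and scope, is committed to the planned analyses with no exemption for the primary contrast. Under the arm-level reading the effect cannot be estimated. Under the patient-level reading the contrast need not be the effect of assignment.

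Confidence is high that the rule should not govern the primary analysis, and low to moderate on the size and direction of bias. Over the models examined at an assumed 25% vs 12%, the shift runs from about −0.1 to +0.5 points against a 2.0-point target. It is immaterial if drop-out is equal. In the single-time-point model it is also nil if drop-out is unrelated to pain. The false-benefit rates of 4.5 to 11% belong to that model alone and should not be read as the trial's error rate. This should be fixed before analysis.

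**What to change.** Delete the drop-out covariate clause from the fidelity section, or confine it to a labelled sensitivity analysis that does not replace the primary estimate. Keep the comparison of drop-out rates. Report session drop-out for the two session arms and loss to follow-up for all three arms separately. Handle differential loss with the multiple imputation already planned. A sensitivity analysis allowing data to be missing not at random is a low-cost option, with the method left to the trial statistician.

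The deletion is a wording change. The optional sensitivity analysis is modest extra work on data already collected. The 107 per arm, 402 enrolled and stated 91% power are unaffected.

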Although it is possible that depressive symptoms could interfere with treatment efficacy, it is also possible that those with depressive symptoms might benefit more from the treatment than those who are not depressed, given that the intervention teaches skills that can help in the treatment of depression. By excluding only the participants with severe depressive symptoms, and including patients with other levels of depressive symptoms, generalizability will be enhanced and we will be able to determine if the intervention is more or less effective among persons with depressive symptoms, relative to non-depressed persons. In our pilot study of 112 knee arthroplasty patients with high pain catastrophizing as defined in our trial, a total of 3 patients (2.7%) had PHQ scores of 20 or higher. Depressive symptoms will be examined as a potential moderator of treatment effect in the analysis.

Other exclusion criteria were selected to reduce the risk of confounding in the trial. For example, patients receiving revision surgery have poorer outcomes as compared to patients undergoing primary knee arthroplasty.⁵⁶ Screening will be conducted via telephone by study staff after the patient has consented for surgery.

Randomization and Blinding

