[name] has led and completed two published studies of the relationship between psychological distress and outcome following knee arthroplasty. The first was a secondary analysis of a cohort study of 952 patients and was published in 2007.⁹² Our findings suggested that surrogate measures of general psychological distress (like the mental health score of the SF-36) did not provide adequate fidelity and that more precise measures of specific psychological states and disorders were necessary.

To test this hypothesis a second study was undertaken to determine if more specific measures of psychological distress (i.e., depression, anxiety, self-efficacy, fear of movement, pain catastrophizing) predict pain and functional outcomes following knee arthroplasty.²⁹ After adjusting for confounding factors, pain catastrophizing was the only consistently strong psychological predictor of poor WOMAC Pain outcome (Odds ratio = 2.7, 95%CI=1.2, 6.1). We found that 60% of patients with high pain catastrophizing had a poor outcome, (defined as a WOMAC Pain change score of <50% from baseline to 6 months post surgery) as compared to 30% of patients with low catastrophizing who had poor outcome. Other studies have reported similarly strong findings indicating that pain catastrophizing predicts pain and function outcome following knee arthroplasty.^{27,28,30,31}

Pilot Intervention Study

The research team recently completed a quasi-experimental study of the efficacy of the proposed pain coping skills intervention.⁶⁹ We recruited 18 knee arthroplasty patients from two sites (Duke University and Virginia Commonwealth University) to participate. All patients met the inclusion criteria as defined in our proposed trial and received the pain coping skills training intervention. WOMAC Pain and Disability scores and PCS scores were collected prior to surgery and 2 months following surgery. Data from patients receiving pain coping skills training were compared to a historical cohort of 45 patients who also received knee arthroplasty and had high pain catastrophizing (≥ 16 on PCS), but received no pain coping skills training. ANCOVA adjusting for baseline scores was used to compare the patients in the treatment group to the historical cohort. The Group (coping skills training vs usual care) X Time (pre-op vs follow-up) interaction was used to estimate the magnitude and significance of the treatment effect.

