Patients in the pain coping skills group demonstrated a mean improvement in WOMAC Pain scores of 6.9 (sd = 4.7) points while patients in the historical cohort achieved a mean improvement of 2.6 (sd = 4.8) points. Differences among groups were highly significant with effect sizes ranging from .71 to .96. for WOMAC Disability, WOMAC Pain and Pain Catastrophizing.

Respondent burden was assessed by asking participants to complete a 16-item questionnaire (2 items for each coping skill) that assessed the extent to which each skill was helpful and how frequently the skills were used. Patients rated each skill as being somewhat to extremely helpful and patients indicated they used each skill at least weekly to more than once per day. These data suggest that patients found the skills to be therapeutic and useful during their recovery.

In summary, our preliminary work and the work of others^{27,28,31,39} strongly suggest that: (1) pain catastrophizing is a key psychological variable that adversely impacts pain and functional outcomes in patients following knee arthroplasty; (2) our proposed intervention has strong potential for producing clinically important improvements in self-reported pain and functional status in patients who are at high risk for poor outcome; and (3) the feasibility of the intervention is high and can be delivered efficiently in multiple sites.

Pilot Physical Performance Battery Study

We undertook a second pilot study to determine the feasibility of using a well defined physical performance battery for patients following knee arthroplasty. Associations between self-report and performance measures are moderate, on the order of $r = .5$, suggesting they measure different patient attributes.⁹³⁻⁹⁷

Because there is no agreed upon standard set of performance-based measures for patients with knee arthroplasty, we chose to pilot a six-minute walk test a measure that is reliable and captures changes in distance walked and pain perceived throughout the recovery period.^{93,94,98} The Short Physical Performance Battery (SPPB) combines two simple balance tests a 4-meter walk test and a repeated chair stand test into one summated score. The SPPB has been studied extensively and found to be significantly reduced in persons with knee arthritis as compared to healthy age-matched persons⁹⁹ and is responsive to changes following interventions designed to improve mobility.^{100,101}

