We recruited a consecutive series of 10 patients 1 year following knee arthroplasty to determine if the SPPB and the six minute walk test would be well tolerated. In addition, we were concerned about possible ceiling effects on the SPPB which can occur with high functioning elderly persons.¹⁰² SPPB total scores range from 0 to 12. The mean score on the SPPB summary scale for the patients was 8.5 (sd = 2.3) and ranged from 3 to 11. We concluded that the SPPB and the 6-minute walk test are well tolerated by patients receiving knee arthroplasty and that some individual tests comprising the SPPB will likely demonstrate ceiling effects. We will therefore use the composite SPPB score and a time-based calculation of the composite SPPB score¹⁰³ in addition to the 6-minute walk test.

Primary and Secondary Outcome Measures and Endpoints

Participants from all three arms will be evaluated by an assessor who is blinded to group allocation at baseline, 1 week prior, and 1 week after, 2 months, 6 months and 1 year after surgery. The baseline assessment will include age, gender, comorbidity^{14,104}, education and occupation, current medications, mental healthcare received and a variety of pain and psychological characteristics including depression, anxiety, pain coping etc. Follow-up outcomes will include measures of pain, function, catastrophizing and depression. (see MOOP in appendix for a complete description).

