The primary outcome measure and endpoint will be the WOMAC Pain scale measured 1 year following knee arthroplasty.¹⁰⁵⁻¹⁰⁹ The WOMAC has been studied extensively and its scales have been shown to be reliable and valid for quantifying the extent of both pain and disability in patients undergoing knee arthroplasty.^{16,110,111} Secondary outcome measures will be the WOMAC Disability scale, Pain Catastrophizing Scale (PCS),¹¹²⁻¹¹⁴ a verbal pain rating scale,^{115,116} and a patient global rating of change scale measured on a numerical rating scale from -5 (vastly worse) to +5 (completely recovered) and measured 2 months, 6 months and 1 year post-surgery.¹¹⁷⁻¹¹⁹ The timeframes were chosen because the trajectory of recovery following knee arthroplasty is non-linear and we want to track changes associated with the intervention during the course of the study.^{10,13,94} Two performance-based measures, the 6-minute walk test^{93,98} and the Short Physical Performance Battery will be assessed at baseline and 1 year post-surgery.¹²⁰ Routine follow-up visits are typically scheduled with the surgeon at 12 months following surgery. Planning follow-up measures to coincide with routine patient visits to their surgeon or other provider will be a cost-effective and clinically feasible way of collecting follow-up data with minimal burden. All sites will have the space necessary to conduct the performance-based tests. This is the first study of a pain coping skills training intervention that has used performance-based measures to assess efficacy. This battery of primary and secondary outcomes addresses the key domains of outcomes recommended by IMMPACT, a consensus based group of experts in the area of pain treatment outcomes.^{121,122}

Sample Size Estimations

The primary endpoint will be the WOMAC Pain score at 1 year. Changes of 2 or more points in the 20 point WOMAC Pain scale indicate clinically important differences between individual patients.¹²³⁻¹²⁶ We powered our study to detect a difference of at least 2 points between the pain coping skills group and the arthritis education group. Our pilot study showed a larger difference of 4.2 points (with an effect size of .74) between the coping skills group and the usual care group two months following surgery. We will use a more conservative treatment

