effect of 2 WOMAC Pain points for coping skills training for three reasons. First, our pilot study used a quasi-experimental design which may overestimate treatment effects because of non-randomization. Second, estimates were based on comparisons to usual care, and we suspect that some therapeutic benefit will be experienced by the arthritis education group. Third, these data represent only short-term changes following surgery and most patients continue to improve up to a year following surgery.^{9,14}

Using a two-sided two group 0.05-level t-test of differences in means and assuming the intervention difference minus the arthritis education control difference is at least 2.0 WOMAC Pain points, a sample size of 107 in each group will have 91% power to detect this difference, assuming that the common standard deviation is 4.34 (based on pilot work described earlier). This corresponds to an effect size of 0.46 which is consistent with the effect of other behavioral interventions for knee arthritis.¹²⁷⁻¹²⁹ This sample size also adequately powers the study to detect a 20% difference between groups in the number of patients with a 50% or greater improvements in WOMAC pain relative to baseline scores.^{9,10,12-15,130} This effect will be equivalent to an odds ratio of 2.25 and is equivalent to a Numbers Needed to Treat (NNT) of 5 which is indicative of an effective intervention.¹³¹ The revised CONSORT statement endorses use of indexes such as number needed to treat.¹³²

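### The SD of 4.34 behind the stated 91% power does not match the pilot work named as its source; the printed pilot SDs (4.7 and 4.8) give about 86% for the t-test described

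*Combined protocol and SAP*

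**What the plan says.** Sample Size Estimations sets the endpoint: "The primary endpoint will be the WOMAC Pain score at 1 year". The calculation is a two-sided two-group t-test at the 0.05 level with 107 patients per arm. The quantity tested is a difference in change: "the intervention difference minus the arthritis education control difference is at least 2.0 WOMAC Pain points". The stated power is 91% and the stated effect size 0.46, "assuming that the common standard deviation is 4.34 (based on pilot work described earlier").

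Three pieces of pilot work are described before that sentence:

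- The eligibility discussion under Participants mentions "our pilot study of 112 knee arthroplasty patients with high pain catastrophizing as defined in our trial", and reports only a count of patients with severe depression.
- Pilot Intervention Study compares 18 treated patients with 45 historical controls. The treated group had a "mean improvement in WOMAC Pain scores of 6.9 (sd = 4.7) points", and the controls "achieved a mean improvement of 2.6 (sd = 4.8) points". On timing: "WOMAC Pain and Disability scores and PCS scores were collected prior to surgery and 2 months following surgery". The comparison was analysed by ANCOVA on baseline.
- Pilot Physical Performance Battery Study prints an SD for a different measure: "The mean score on the SPPB summary scale for the patients was 8.5 (sd = 2.3").

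Sample Size Estimations also reports the 18 versus 45 comparison as 4.2 points with an effect size of 0.74.

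Data Analysis specifies a linear mixed model with repeated times that accounts for baseline covariates, and estimates effects by contrasts of mean change from baseline. It does not name baseline WOMAC Pain as a covariate.

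**The concern.** The plan names its source for the SD, so the source can be checked. Only one of the three pilots prints an SD for WOMAC Pain. Its SDs are for change from baseline, the same kind of quantity as the difference being powered. Both exceed 4.34, and a pooled SD must lie between its two components, so 4.34 cannot be obtained by pooling them. The figure appears nowhere else and no derivation is given.

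At stake is the stated chance of detecting a true 2-point effect on the primary endpoint, and the effect size of 0.46 that the section uses to claim consistency with other behavioural trials.

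**Working it through.** **Inputs.** From Sample Size Estimations: n = 107 per arm, difference 2.0, two-sided alpha 0.05, SD 4.34. From Pilot Intervention Study: SD 4.7 (n = 18) and SD 4.8 (n = 45).

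**Formula.** Power from the noncentral t with 2 × 107 − 2 = 212 degrees of freedom and noncentrality 2.0 / (SD × √(2/107)).

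**The plan's own figure.** At SD 4.34 the noncentrality is 2.0 / (4.34 × 0.1367) = 3.37 and power is 91.9%. The effect size is 2/4.34 = 0.46. Both agree with the plan.

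**Pooled pilot SD.** √((17 × 4.7² + 44 × 4.8²)/61) = 4.77. Its 95% confidence interval (chi-square, 61 df) is 4.06 to 5.80.

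**Power with other SDs, 107 per arm, unadjusted:**

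| SD | Where it comes from | Effect size | Power |
|---|---|---|---|
| 4.1 | near the lower confidence limit | 0.49 | 94% |
| 4.34 | plan | 0.46 | 91.9% |
| 4.7 | pilot, treated group | 0.43 | 87.3% |
| 4.77 | pilot, pooled | 0.42 | 86.2% |
| 4.8 | pilot, historical cohort | 0.42 | 85.9% |
| 5.2 | where power reaches 80% | 0.38 | 80% |
| 5.68 | 4.2/0.74 | 0.35 | 73% |
| 5.8 | upper confidence limit | 0.34 | 71% |

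Power of 91% needs an SD of 4.41 or less. At SD 4.77, 107 per arm gives 91% power for a difference of 2.16 points, not 2.0.

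**The second pilot figure.** 4.2/0.74 = 5.68. With the pooled change SD the effect size would have been 4.2/4.77 = 0.88, so the 0.74 was evidently standardised by something else, which the section does not define.

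**Could 4.34 be baseline-adjusted?** Assume equal SDs before and after surgery (call it σ) and a pre-post correlation r. The change SD is σ√(2(1 − r)) and the ANCOVA residual SD is σ√(1 − r²), so residual SD = change SD × √((1 + r)/2). Starting from 4.77:

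| r | Residual SD | Power |
|---|---|---|
| 0.5 | 4.13 | 94% |
| 0.6 | 4.27 | 93% |
| 0.7 | 4.40 | 91% |
| 0.8 | 4.53 | 90% |

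A residual SD of 4.34 corresponds to r = 2 × (4.34/4.77)² − 1, about 0.65. The documents print no correlation, so this is an assumed range and not an estimate.

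**The case against.** The best defence is that 4.34 may well come from the pilot after all. That study was analysed by ANCOVA on baseline, and an adjusted SD is normally smaller than the change-score SD. The correlation needed, about 0.65, is unremarkable, and the full pilot report is cited rather than reproduced. This stands as a possible explanation. It does not remove the gap, because the power statement describes a plain two-group t-test on differences and mentions no adjustment.

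A second defence is sampling error. 4.34 lies well inside the interval from 4.06 to 5.80, and 4.77 is itself a value from a small, non-randomised, 2-month comparison, no better validated for 1 year. That also stands, but the plan presents 4.34 as what the pilot gave, not as a choice within an interval, and the same interval reaches down to about 71% power.

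A third is that the t-test is a planning simplification for a mixed model with baseline covariates, in a design where stratification is expected to reduce variability. That is fair, but the gain counted above depends on baseline WOMAC Pain being in the model, and the text does not say that it is.

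A reader might infer more: that the 91% is a calculation error, or that the trial is underpowered and needs more patients. The documents support neither. The figure reproduces for its stated SD, no separate power target is given, and power stays at or above 80% up to an SD of about 5.2.

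**Conclusion.** The concern holds as an unsupported input, not as an arithmetic error. For the test described, the printed change-score SDs give about 86% power instead of 91%. The chance of missing a true 2-point effect is then about 14% instead of 9%, and the effect size is 0.42 instead of 0.46. The plan's other pilot figure points further away from 4.34, to about 73%, but its undefined standardiser means that it cannot be relied on.

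The 86% rests on two assumptions: that the 2-month pilot SDs carry over to 1 year, and that the comparison is unadjusted. With adjustment for baseline WOMAC Pain and equal pre and post SDs, the same pilot SD gives about 90% to 94% for correlations from 0.8 to 0.5. So a power near 91% is attainable, but the plan as written does not show it. This should be fixed.

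**What to change.** 1. In Sample Size Estimations, take one of two routes.
   - State the power of the unadjusted change-score t-test as about 86% (SD 4.77, pooled from 4.7 with n = 18 and 4.8 with n = 45; effect size 0.42), labelled as unadjusted. Add a sensitivity range: about 94%, 92%, 86%, 80% and 71% at SDs of 4.1, 4.34, 4.8, 5.2 and 5.8. Note that the SDs are 2-month pilot values while the endpoint is at 1 year.
   - Or, if 4.34 is a baseline-adjusted SD, say so, show its derivation, and describe the 91% as the power of a baseline-adjusted comparison.
2. On either route, define the standardiser behind the 0.74 effect size and reconcile it with the SD used.
3. In Data Analysis, name baseline WOMAC Pain as a covariate for the 1-year primary contrast, with the post-baseline scores as the repeated outcome. Alternatively, keep baseline among the repeated outcomes and constrain its mean to be equal across arms. Without one of these, a contrast of change from baseline in the repeated-measures model need not deliver the adjustment. If the first route is taken in step 1, the 86% is then a cautious planning figure for a more efficient analysis, and the text should say so.

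The cost is a few sentences and one named covariate that the trial already collects. No extra patients are needed. The only downside is a slightly lower stated power if the unadjusted figure is used.
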